9.6 Data Management

Physician should complete the CRFs, sign and date the CRFs accurately. All CRFs must be legible and completed in indelible ballpoint ink. Corrections to the CRFs should be made with a single line, be initialed and dated, with the reason for changes given. Data are not to be obliterated by blacking out, correction fluid, or by erasing the original entry.

At the conclusion of the study, the completed signed and dated case report forms for the enrolled patients should be provided to the AbbVie Korea by the physician for every patient enrolled in the study. As distinct case report form should be created for each unique instance when data is to be collected ONLY data specified in the protocol should be collected and submitted to AbbVie Korea.

CRAs or their designees will be responsible to review the collected CRFs for completeness and conclusiveness.

The data entered by the physician will be reviewed by CRAs or their designees and when necessary, query will be generated to correct the data by the physician. After completion of the data review, data will be locked to prevent further editing.

9.7 Data Analysis

Justification for the planned sample size

Information on at least 600 subjects will be collected in this surveillance study in accordance with the Korean regulations on New Drug Re-examination (i.e. New Drug Re-examination Standards: Ministry of Food and Safety (MFDS)).

The sample size of 600 has been selected in order to give at least 95% probability of detecting at least one uncommon SAE that occurs in the Korean patient population at a rate of at least 0.5%. This estimate is based on the assumption that the occurrence of AEs has a Poisson distribution and that if the population rate of occurrence of an AE is 0.5% then the expected number of AEs in the proposed sample size of 600 would be 3. The probability of observing 1 or more events with a Poisson parameter of 3 is 0.95 or 95%.

If we have an AE with a population probability of 0.5% then the expected number of events in a sample size of 600 will be 3. Using the Poisson Distribution with a parameter of 3 the probability of getting zero AEs in our sample size of 600 is given by the formula:

$$\Pr\{X = 0\} = \frac{3^0 \times e^{-3}}{0!} = 1 \times 0.0498 = 0.0498$$

The probability, therefore, of having 1 or more AEs in that sample size is $1 - 0.0498 = 0.9502$.

At least 600 subjects were to be collected for surveillance to meet the local regulatory requirements, but number of subjects to be enrolled was adjusted to 141 subjects. (Refer to section 9.5)

Analysis Population

Number of collected and analyzed patient will be presented as following items: Contracted cases, collected number of CRFs, safety-evaluable cases, effectiveness-evaluable cases, number of drop-out cases, Reasons for drop-out

The safety analysis data set will include all subjects who have received at least one administration of Humira® following the initiation of surveillance and have completed follow up for the safety information.

For induction effectiveness of Humira®, the effectiveness analysis data set will include all subjects who have been administered Humira® and prescribed Humira® for 4 weeks including induction period (± 1 week) and for whom effectiveness evaluation parameters have been recorded. And for maintenance effectiveness of Humira®, effectiveness analysis data set will include all subjects who have been administered Humira® and prescribed Humira® for 6 months (± 4 weeks) and for whom effectiveness evaluation parameters have been recorded. The subjects whose effectiveness evaluation was not properly conducted because their data from evaluation parameters were missing or they discontinued administration prior to the effectiveness evaluation will be excluded from the evaluation.

Safety Analysis

The adverse events will be coded by MedDRA dictionary. The number and percentage of subjects reporting any serious adverse events/adverse drug reactions will be tabulated overall and by MedDRA 17.0 or more recent version, in preferred term. The number and percentage of subjects reporting unexpected (unlabeled) adverse drug reactions will be tabulated in a similar fashion.

To investigate the factors affecting the safety, the number and percentage of subjects reporting adverse events will also be classified by various background factors (e.g., demographic factors, treatment factors such as medical history, dosing and administration, concomitant medications, beginning of administration before/after the registration date, etc.) and tabulated. If the incidence of adverse events in the subjects who began the administration before/after the registration date has statistical significance, it will be presented as a separate item. In addition, if there are patients who have already been

administered Humira® when participating in the surveillance, their adverse events from the first administration of Humira® to the inclusion will be presented in a separate table. If data from special patient groups are collected, they will be extracted and tabulated separately for adverse events/adverse drug reactions.

Effectiveness Analysis

The effectiveness assessment of Humira® induction therapy and maintenance therapy will be presented by the number and percentage of the subjects with clinical response. Clinical response is defined as decrease in PCDAI score from baseline by ≥ 15 points and if CDAI score is collected, Clinical response is defined as decrease in CDAI score from baseline by ≥ 70 points.

To investigate the factors affecting the effectiveness, the number and percentage of subjects with clinical response will also be classified by background factors (e.g., demographic factors, treatment factors such as medical history, dosing and administration, concomitant medications, beginning of administration before/after the registration date, etc.) and tabulated. If the effectiveness evaluation of above factors has statistical significance, it will be presented as a separate item.

Statistical Methods

The descriptive statistics for safety and effectiveness parameter in each year will be presented in annual reports.

In final report (Re-examination report), safety and effectiveness outcome by background factor will be summarized and analyzed. The analysis for categorical variables will be performed using chi-square test or fisher's exact test and continuous variables will be performed using Wilcoxon rank sum test or t-test. Also, incidence rate of adverse event collected in overall PMS period will be analyzed and 95% CI will be presented.

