4.0 Abstract

Title: Post-Marketing Surveillance of Humira® in Korean Pediatric CD Patients under the “New-Drug Re-examination”
Rationale and Background: This non-interventional, observational study will be conducted in compliance with the New Drug Re-examination Guideline in Korea
Research Question and Objectives: To evaluate the safety profile of Humira® for Pediatric CD patients in normal medical practice: (1) Serious adverse event•adverse drug reaction (2) Unexpected adverse event•adverse drug reaction (3) Already known adverse drug reaction (4) Non-serious adverse drug reaction (5) Adverse events resulting from drug misuse, drug abuse or drug interaction (6) Other information related to the product’s safety and effectiveness (including the influence to the laboratory value)
Study Design: Post-Marketing Surveillance
Population: Pediatric CD patients who have been prescribed Humira® by the treating physician
Variables: Demographics, Medical History, PPD Skin Test, Chest X-ray, Interferon Gamma Release Assay, Concomitant Medication, Safety, PCDAI score (CDAI score if it is evaluated)
Data Sources: paper Case Report Form
Study Size: 141 patients
Study Duration : 12 Sep 2013 ~ 11 Sep 2017
Data Analysis: (1) The safety analysis data set : all subjects who have received at least one dose of Humira® during the study and have been followed up for the safety information (2) The effectiveness analysis data set: 
Effectiveness of Humira® induction therapy: all subjects who have been administered Humira® and received Humira® for 4 weeks including induction period (± 1 week) and for whom effectiveness evaluation parameters have been recorded.Maintenance effectiveness of Humira®: all subjects who have been administered Humira® and received Humira® for 6 months (± 4 weeks) and for whom effectiveness evaluation parameters have been recorded.
Milestones: (1) Start of Data collection : 1Q 2015 (2) End of Data collection : 3Q 2017 (3) Final Report of Study Results : 4Q 2017

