† The mean number of patients: The number of patients prescribed with anti-TNF agents for relevant disease codes (K500, K501, K508 or K509); source: Health Insurance Review & Assessment Service; unit: people

‡ Percent: calculated by dividing the mean number of patients by the number of patients diagnosed

3) Difficulties in getting patients' consents

Pediatric CD is indicated for pediatric patients, it is difficult to get pediatric patients' consents from their parents.

However, we will make every effort to enroll maximum number of subjects. We expect maximum 141 patients will be recruited [Table 2].

[Table 2] The number of subjects expected to be enrolled in this study

Classification	No. of subjects
Enrolled subjects as of October, 2016	100
- subject who start Humira treatment after enroll in the study	71
- subject who starts Humira treatment before enroll in the study	29
Estimated No. of subjects to be enrolled	Approx. 41
- subject who will start Humira treatment after enroll in the study	31*
- subject who starts Humira treatment before enroll in the study	10
Total	Approx. 141

* Calculated as follows: 5.07 (mean number of newly diagnosed patients per month) x 6 months (remaining enrollment period) = 30.42

About 15 investigators across the country will be participating in this surveillance and the number of subjects to be collected by each investigator will vary.

Study Duration

The study duration designated by MFDS is from 12 September 2013 to 11 September 2017. The study will start after the launch of the product as a new drug for pediatric CD and the final report will be submitted to MFDS by 11 Dec 2017. Interim study reports will be submitted to MFDS every 6 months for the first 2 years, then annually thereafter during PMS period.

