9.9 Limitations of the Research Methods

Open-label data from non-randomized patients; reporting bias with historical safety data.

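### Section 9.7 still plans for and justifies 600 subjects; for the 141 now planned, the plan's own formula gives at best about a 51% chance of seeing an SAE with a 0.5% rate, and no figure for 141 is stated

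*Combined protocol and SAP*

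**What the plan says.** Under its sample-size justification, section 9.7 opens with a commitment in the future tense: "Information on at least 600 subjects will be collected in this surveillance study". It then gives the statistical reason: "The sample size of 600 has been selected in order to give at least 95% probability of detecting at least one uncommon SAE", where the SAE occurs at a rate of at least 0.5%. The supporting calculation is a Poisson one with a parameter of 3, which gives 0.9502.

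The last paragraph of the same subsection says that the "number of subjects to be enrolled was adjusted to 141 subjects" and refers to section 9.5. The abstract agrees: "Study Size: 141 patients". Section 9.5 gives the reasons for the reduction: low incidence and prevalence, the drug not being a primary therapy, and difficulty obtaining consent. It adds a recruitment projection and concludes: "We expect maximum 141 patients will be recruited".

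Three other places bear on the point:

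- The analysis-population text in section 9.7 limits the safety set to treated subjects who "have completed follow up for the safety information".
- The statistical methods in section 9.7 promise that the "incidence rate of adverse event collected in overall PMS period will be analyzed and 95% CI will be presented".
- Section 9.9 lists the limitations in one line: "Open-label data from non-randomized patients; reporting bias with historical safety data". The reduced size is not among them.

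**The concern.** Amendment 2 changed the number of subjects but not the statistical argument attached to it. Section 9.7 therefore holds two statements of size, and the only statement of what the surveillance can detect belongs to the size that will not be reached. The feasibility reasons in section 9.5 explain why 600 is out of reach, but not what 141 can show.

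This matters because of what the study is for. Serious and unexpected adverse events head the objectives in section 8.0, the hypothesis there is a safety profile consistent with the phase 3 studies, and section 7.0 plans a comparison with the label. The absence of a particular SAE will therefore be interpreted. A reader who takes the 95% figure at face value would treat no cases as good evidence against a 0.5% rate. With 141 subjects it is weak evidence.

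**Working it through.** **Inputs**

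- Event rate 0.5%, target probability 95%, Poisson model with parameter n × rate: section 9.7.
- n = 600: section 9.7. n = 141: abstract, section 9.5 and section 9.7.
- 100 subjects already enrolled as of October 2016: section 9.5, Table 2.
- 71 + 31 = 102 subjects who start treatment after enrolment: section 9.5, Table 2.
- The plan gives no non-evaluable rate. Losses of 10% and 20% are assumed here to show a range: 141 × 0.9 ≈ 127 and 141 × 0.8 ≈ 113.

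**Step 1: reproduce the plan's figure.** At n = 600, expected events are 600 × 0.005 = 3, and P(at least one) = 1 − exp(−3) = 0.9502. This matches section 9.7 (exact binomial 0.9506).

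**Step 2: the same formula at the planned size.** At n = 141, expected events are 141 × 0.005 = 0.705, and P(at least one) = 1 − exp(−0.705) = 0.506. The exact binomial, 1 − 0.995^141, gives 0.507.

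**Step 3: rate seen with 95% probability.** Solving 1 − exp(−n × rate) = 0.95 gives rate = −ln(0.05)/n. For 600 this is 0.50%; for 141 it is 2.12%.

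**Step 4: what zero events would exclude.** The exact (Clopper-Pearson) two-sided 95% upper limit for 0/n is 1 − 0.025^(1/n). For 600 this is 0.61%; for 141 it is 2.58%.

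**Step 5: smaller numbers.**

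| n | Basis | P(at least one) at 0.5% | Rate seen with 95% probability | Two-sided 95% upper limit, 0 events |
|---|---|---|---|---|
| 600 | superseded size | 0.950 | 0.50% | 0.61% |
| 141 | planned maximum | 0.506 | 2.12% | 2.58% |
| 127 | assumed 10% loss | 0.470 | 2.36% | 2.86% |
| 113 | assumed 20% loss | 0.432 | 2.65% | 3.21% |
| 102 | start treatment after enrolment | 0.400 | 2.94% | 3.55% |
| 100 | enrolled by October 2016 | 0.393 | 3.00% | 3.62% |

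The last two columns differ because the detection criterion puts all 5% in one tail, whereas a two-sided 95% interval puts 2.5% there. The row for 102 matters because section 9.7 puts the adverse events that prior starters had before inclusion in a separate table. The row for 100 is a mid-recruitment count and serves only as a low reference point.

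**The case against.** The strongest reply is that the document largely resolves the conflict itself. The subsection that states 600 closes by saying, in the past tense, that 600 had been the requirement and is now 141, with a cross-reference; section 9.5 and the abstract agree. Nobody would recruit or report to 600, and no decision rule depends on the 95% figure. That is fair, and it rules out any suggestion of concealment. It does not supply the missing figure: if the 600 text is read as history, the plan makes no statement at all about what 141 subjects can detect.

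Second, the final report will give adverse event incidence with a 95% CI, which for an event with no cases would yield an upper limit. This is a partial answer. The plan does not name the interval method or say that an interval will be given for each event type, including those with no cases. An interval reported afterwards also leaves the detection claim in section 9.7 uncorrected.

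Third, the safety set may lose few subjects. Section 9.2 counts drop-outs whose safety information is obtained, including by telephone or correspondence, and the abstract is worded more broadly than section 9.7. This stands: the assumed 10% and 20% losses have no basis in the plan and serve only as a range. A broader set still cannot raise the figure above that for 141.

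Fourth, giving both 2.1% and 2.6% offers two thresholds for nearly the same question, and the plan does not prescribe a two-sided exact limit. The two figures need clear labels. The first restates the plan's own criterion; the second is the zero-event limit of a two-sided 95% interval, calculated here by the exact method.

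**Conclusion.** The concern holds and should be fixed. Section 9.7 states a size and a detection probability that the current design does not deliver, and nothing in the plan replaces them. An SAE with a true rate of 0.5% would go unseen about half the time (1 − 0.506 = 0.494) if all 141 subjects are evaluable, against about 5% of the time at 600. Detection with 95% probability needs a rate of about 2.1% or more, roughly four times the stated 0.5%.

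These figures rest on the plan's own Poisson model and 0.5% rate; the exact binomial gives nearly the same answer. They are a ceiling, because 141 is the expected maximum. Only the rows for 127 and 113 depend on assumed losses. The point concerns what the plan claims; it does not dispute the decision to reduce the size to 141.

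**What to change.** In section 9.7, mark the 600-subject sentence and its calculation as superseded by Amendment 2, and add text along these lines:

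> With 141 subjects, the probability of observing at least one event with a true rate of 0.5% is about 51%. A probability of 95% is reached only for rates of about 2.1% or more. If no events are observed, the exact two-sided 95% upper limit is about 2.6%. These figures will be recalculated in the final report for the number of subjects in the safety analysis set.

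In section 9.9, add:

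> Because of the reduced size, absence of an event does not exclude rates below about 2.6%.

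The 2.6% in section 9.9 should be updated in the final report together with the section 9.7 figures. Section 9.2 needs no change on this account.

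The cost is wording and a one-line calculation, with no extra patients, visits or data. The stated detection capability becomes less favourable, but it then matches the study being run.

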9.2 Setting

Selection of Study Population

Pediatric CD patients who has been prescribed Humira® by the treating physician as per Korean label will be enrolled.

The patients who are receiving Humira® for pediatric CD during study period and meet the inclusion /exclusion criteria will be enrolled in the sites which signed a contract with AbbVie.

Once the study agreement is in place, the surveillance will be initiated at the site, and all patients who are prescribed Humira® for pediatric CD treatment during the surveillance period and who meet the inclusion /exclusion criteria will be enrolled in the study until the assigned number of subjects are registered at the site.

Inclusion Criteria

1. Pediatric patients with Crohn's Disease who are prescribed Humira in accordance with the Korean label for Humira authorization (labeling)
2. Patients who have given written authorization or patients whose legal representatives have given it to use their personal health data for the purposes of this study.

Physician will refer to the product market authorization (label) for inclusion criteria.

Exclusion Criteria

Patient with any of the following should not be registered in this surveillance:

1. Any contraindications to Humira as listed on the approved product market authorization (labeling)
2. Patients who is participating on other clinical trials.

Patients will be observed for 6 months following first dose of Humira®.

It is planned to include all patients who are treated with Humira® until the planned number of cases are collected to obtain meaningful safety data including TB incidence in the early stage of the study conduct. Once this study has been initiated in an institution, physicians are recommended to include/recruit all eligible patients who are prescribed Humira®.

An evaluable patient is a patient who has been administered Humira® at least once and has safety information at subsequent visits. (or telephone contact, correspondence)

Drop-out patients also will be considered for safety evaluation, if the safety information is obtained by follow-up contact. If there is loss of follow-up, the reason will be recorded.

Investigator Selection Criteria

The surveillance will be conducted in medical institutions in Korea. The institutions include clinics and hospitals. The physician must meet the following criteria:

1. A physician who is working in a hospital or clinic and has a patient pool eligible for this surveillance.

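### The 6-month response rate counts only children still on Humira with a recorded score, and no analysis with a wider denominator is planned

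*Combined protocol and SAP*

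**What the plan says.** Section 9.7 (Analysis Population) defines two effectiveness sets, one for induction (4 weeks ± 1 week) and one for maintenance (6 months ± 4 weeks). Each requires Humira for the period and recorded effectiveness parameters. Subjects with missing data are left out, and so are those who "discontinued administration prior to the effectiveness evaluation will be excluded from the evaluation". The Abstract has the same restriction in effect: its maintenance set is subjects who "received Humira® for 6 months (± 4 weeks) and for whom effectiveness evaluation parameters have been recorded".

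Under Effectiveness Analysis, the result "will be presented by the number and percentage of the subjects with clinical response", with response defined as a fall from baseline of at least 15 PCDAI points, or at least 70 CDAI points where CDAI is collected. The plan adds that "the number and percentage of subjects with clinical response will also be classified by background factors", including whether Humira was started before or after registration. Statistical Methods names chi-square or Fisher's exact tests for categorical outcomes by background factor.

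For disclosure, section 9.7 lists counts of contracted cases, collected forms and safety-evaluable cases, then "effectiveness-evaluable cases, number of drop-out cases, Reasons for drop-out". For safety, section 9.2 states: "Drop-out patients also will be considered for safety evaluation, if the safety information is obtained by follow-up contact". Section 9.7 limits the safety set to dosed subjects who "have completed follow up for the safety information".

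No all-treated denominator, non-responder rule, imputation or other sensitivity analysis for effectiveness appears anywhere. Section 9.9 does not list this selection among the limitations.

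**The concern.** Being on drug at 6 months can itself depend on response. A child who stops for lack of effect leaves both the numerator and the denominator of the 6-month rate instead of counting as a failure. This follows from a stated rule, not from a missing detail.

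Safety is the main objective. Effectiveness enters as item 6 of section 8.0. But the same section also states the hypothesis that the drug will work in Korean children with Crohn's disease, and in this single-arm study the response rates at 4 weeks and 6 months are the planned results that bear on it. The comparisons by background factor use the same sets, since no others are defined, so a factor linked to stopping could look linked to response, or the reverse.

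The concern is mainly about 6 months. A child assessed on drug at week 4 stays in the induction set even if Humira is stopped later.

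**Working it through.** **Figures from the plan.** The plan states no response rate, discontinuation share, number with a pre-treatment score or effectiveness precision, so there is no effectiveness figure to reproduce. On enrolment, section 9.7 says the "number of subjects to be enrolled was adjusted to 141 subjects". Table 2 in section 9.5 agrees: (71 + 29) + (31 + 10) = 141. Of these, 29 + 10 = 39 start Humira before enrolment.

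**General relation.** Let d be the share excluded, p the response rate in those analysed and q the rate in those excluded.

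The rate over everyone is (1 − d)p + dq, so overstatement = p − [(1 − d)p + dq] = d(p − q).

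In percentage points, with p = 70% assumed:

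| q | d = 10% | d = 20% | d = 30% |
|---|---|---|---|
| 0% | 7 | 14 | 21 |
| 35% | 3.5 | 7 | 10.5 |
| 70% | 0 | 0 | 0 |
| 100% | −3 | −6 | −9 |

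The sign depends only on whether excluded children respond less or more often than those analysed.

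**6-month illustration (all counts assumed).** B = 120 subjects with at least one dose and a pre-treatment score (141 is the upper limit), D = 12 discontinued, M = 12 on drug with a missing score, nobody with unknown treatment status. Analysed: A = 120 − 12 − 12 = 96. Responders: R = 67.

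- Planned rate: R/A = 67/96 = 69.8%.
- Discontinuers as non-responders, missing scores excluded: R/(A + D) = 67/108 = 62.0%, lower by 7.8 points.
- All 24 excluded as non-responders: R/B = 67/120 = 55.8%.
- Opposite direction, the 12 discontinuers all responded: (67 + 12)/108 = 79/108 = 73.1%.
- Opposite bound, all 24 responded: (67 + 24)/120 = 91/120 = 75.8%.
- Sampling half-width of the planned rate: 1.96 × √(0.698 × 0.302/96) = 9.2 points.

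**4-week illustration (assumed D = 2, M = 6, A = 112, R = 78).** Planned 78/112 = 69.6%; discontinuers as non-responders 78/114 = 68.4%, lower by 1.2 points; all eight as non-responders 78/120 = 65.0%; all eight as responders 86/120 = 71.7%.

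**What the planned disclosure can recover.** A reader could divide responders by safety-evaluable cases. If all 141 are safety-evaluable, that is 67/141 = 47.5%. Hold the 24 exclusions fixed and vary their cause:

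| Discontinued / missing score | Discontinuers as non-responders | Rough bound |
|---|---|---|
| 24 / 0 | 67/120 = 55.8% | 47.5% |
| 18 / 6 | 67/114 = 58.8% | 47.5% |
| 12 / 12 | 67/108 = 62.0% | 47.5% |
| 6 / 18 | 67/102 = 65.7% | 47.5% |
| 0 / 24 | 67/96 = 69.8% | 47.5% |

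The rough bound does not move. It treats children without a pre-treatment score as failures, omits those without completed safety follow-up, and cannot separate discontinuation from a missing score.

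**The case against.** The strongest case on the other side is that nothing is miscalculated or contradictory. The plan defines an on-drug, observed-case rate, says who is left out, and promises counts of evaluable and drop-out cases with reasons. Section 12.0 says the report will describe the methods. Safety is the purpose of the study, every magnitude above is assumed, and the 7.8-point gap is smaller than the 9.2-point sampling half-width.

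Much of this stands, and it sets the weight of the point. A reader might infer that the plan hides the exclusion; it does not. A reader might also infer that section 9.2 makes the effectiveness rule inconsistent with the safety rule. That goes too far: drop-outs are kept for safety only when information is obtained, and an adverse-event count needs no score at a fixed visit. Nor is the 6-month rate the only effectiveness result, since response at 4 weeks is also planned, with a CDAI version if collected.

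Two parts do not stand. The promised disclosures are not split by cause or time point, so they yield only the rough bound. And a gap smaller than the sampling half-width is no defence, because selection does not average out as numbers grow.

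**Conclusion.** The point holds. The 6-month rate describes response among children on drug with data. It overstates response among enrolled treated children if excluded children respond less often. In the illustration, a reported 69.8% is compatible with anything from 55.8% to 75.8% among the 120 children with a pre-treatment score. The 4-week effect is probably small, because there is less time to stop.

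Confidence is high on the text and moderate on the direction of bias. A reader might infer that the rate is certainly too high. The documents do not support that: they give no data on why or how often children stop, and the bias vanishes if excluded children respond equally and reverses if many stop after responding. A reader might also take the non-responder rate as the corrected value. It is a different quantity, and conservative if some children stop for reasons other than lack of effect.

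Nor would a wider denominator give response among all children ever treated. About 39 of 141 start Humira before enrolment, and children who stopped before they could enrol are in no denominator.

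**What to change.** In section 9.7 and the Abstract:

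- Keep the current sets, labelled *response among subjects on drug with data*.
- Add a supplementary analysis, chiefly at 6 months and also at 4 weeks, in all subjects with at least one dose and a pre-treatment PCDAI score. Do CDAI separately, in those with a pre-treatment CDAI score.
- Count subjects who discontinued before the assessment as non-responders.
- Show subjects on drug with a missing score, and those lost to follow-up with unknown treatment status, both ways: excluded, and as non-responders.
- Report the numbers excluded by cause at each time point, and the number without a pre-treatment score. Show the available stopping reasons beside the table.
- Split the table by start before or after registration, with a note on the roughly 39 of 141 who start before enrolment and on children who stopped before they could enrol.
- State that the analysis was added during the study and before the final analysis. By October 2016, 100 subjects were enrolled, and interim reports and annual effectiveness summaries are part of the plan.

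No new data are needed: treatment dates, pre-treatment PCDAI and action taken for adverse events (section 9.3) and drop-out reasons (section 9.7) are already planned. The cost is wording in two places and one extra table with several rows, plus a lower and possibly conservative rate beside the current one.
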